#### 3.1 Inclusion Criteria

##### 3.1.1 Patients must have histologically confirmed MCL

*Please note: Measureable disease is not required, but will be followed if it exists.*

##### 3.1.2 Patients must have received 4 or more cycles of one of the following prior systemic induction chemotherapy regimens:

- R-CHOP (with or without cytarabine-containing cycles, including "Nordic" and MCL-NET protocols) [1, 2] with or without auto SCT
- R-Hyper-CVAD with or without auto SCT
- Bendamustine + rituximab with or without auto SCT

*Please note:*

- *Patients are allowed to receive combinations of the above regimens*
- *At the time of registration, patients must be at least 14 days out from last dose of cytotoxic chemotherapy, but no more than 120 days. If a patient underwent auto SCT, he/she must demonstrate engraftment (per treating investigator's discretion) and meet all other hematological requirements as outlined in 3.1.8 below.*
- *Patients who progress during induction therapy are not eligible to enroll in this study.*

##### 3.1.3 Patients must have achieved a response to induction chemotherapy (either CR or PR by Cheson 2007 criteria) and be without known progression.

##### 3.1.4 Patients *may* have received prior radiotherapy.

Study Numbers: NU 14H06  
PCI-32765MCL2003

Initial version: September 24, 2014  
AMD 11: ver. date 08.06.2022

- 3.1.5 Patients must be age  $\geq$  18 years.
- 3.1.6 Patients must exhibit an ECOG performance status  $\leq$  2.
- 3.1.7 Patients must demonstrate adequate organ and marrow function (as defined below) documented within 14 days of registration:
  - ANC  $\geq$  1000/mm^3, independent of growth factor support
  - Platelets  $\geq$  100,000/mm^3, or  $\geq$  50,000 in cases of ongoing bone marrow involvement (*In either case, these must be independent of transfusion support*)
  - Total bilirubin  $\leq$  1.5 x upper limit of normal (ULN)
  - AST(SGOT)/ALT(SPGT)  $\leq$  3 x ULN
  - Creatinine clearance  $\geq$  25 ml/min (using the Cockcroft-Gault Equation – See Appendix III)

*Please note: Patients who do not meet the above criteria because of Gilbert's Syndrome are still eligible.*

- 3.1.8 Women of child-bearing potential (WOCBP) and men must agree to use adequate contraception (see below 'NOTE" for details) prior to study entry and for the duration of study participation (see timelines below for women and men). In addition, men must agree not to donate sperm during and after study participation. Should a woman become pregnant or suspect she is pregnant while participating in this study, she should inform her treating physician immediately.

*NOTE: For female patients, these restrictions apply for 1 month after the last dose of study drug. For male patients, these restrictions apply for 3 months after the last dose of study drug.*

*NOTE: A female of child-bearing potential is any woman (regardless of sexual orientation, having undergone a tubal ligation, or remaining celibate by choice) who meets the following criteria:*

- Has not undergone a hysterectomy or bilateral oophorectomy; or
- Has not been naturally postmenopausal for at least 12 consecutive months (i.e., has had menses at any time in the preceding 12 consecutive months).

*NOTE: 'Adequate contraception' is defined as a method that has a low failure rate (i.e., less than 1% per year) when used consistently and correctly and includes implants, injectables, birth control pills with two hormones, some intrauterine devices (IUDs), sexual abstinence (which is defined as refraining from all aspects of sexual activity) or a sterilized partner. If using hormonal contraceptives, such as birth control pills or devices, a second barrier method of contraception (e.g., condoms) must be used.*

*Men must notify the study staff if their partner becomes pregnant while on study treatment or within 3 months of last dose. Women must notify the*

*study staff if they become pregnant while on study treatment or within 1 month of last dose of ibrutinib, and must immediately stop taking the study treatment.*

- 3.1.9 Female patients must have a negative pregnancy test (blood or urine) within 14 days prior to registration.
- 3.1.10 Patients must be willing and able to avoid consuming food and beverages containing grapefruit, Star fruit or Seville oranges (as these contain certain ingredients that inhibit CYP3A4/5 enzymes) while on ibrutinib study therapy.
- 3.1.11 Patients must have the ability to understand and the willingness to sign a written informed consent prior to registration on study.

## 3.2 Exclusion Criteria

- 3.2.1 Patients who have received  $\geq$  7 days of prior ibrutinib or any prior treatment with another BTK inhibitor are not eligible.
- 3.2.2 Patients receiving ongoing treatment with any other investigational agents are not eligible.
- 3.2.3 Patients receiving live/attenuated vaccinations within 4 weeks prior to registration are not eligible.
- 3.2.4 Patients with a *known* CNS involvement of lymphoma are not eligible (CNS staging not required).
- 3.2.5 Patients who have undergone major surgery within 4 weeks prior to registration are not eligible.
- 3.2.6 Patients who have had a prior allogeneic stem cell transplant are not eligible.  
NOTE: If a patient underwent auto SCT, he/she must demonstrate engraftment (per treating investigator's discretion) and meet all other hematological requirements as outlined in 3.1.8 above.
- 3.2.7 Patients diagnosed or treated for malignancy other than MCL are not eligible unless they meet one of the following exceptions:
  - Malignancy treated with curative intent and with no known active disease present for  $\geq$ 3 years before registration and felt to be at low risk for recurrence by the treating physician.
  - Adequately treated non-melanoma skin cancer or lentigo maligna without evidence of disease.
  - Adequately treated cervical carcinoma in situ without evidence of disease.
  - Malignancy is not considered life-threatening in the opinion of the investigator and does not require treatment (for example, low risk

Study Numbers: NU 14H06  
PCI-32765MCL2003Initial version: September 24, 2014  
AMD 11: ver. date 08.06.2022

prostate cancer undergoing active surveillance or low-risk myelodysplastic syndrome not requiring therapy).

- 3.2.8 Patients with a history of stroke or intracranial hemorrhage within 6 months prior to registration are not eligible.
- 3.2.9 Patients who require anticoagulation with warfarin or equivalent vitamin K antagonists are not eligible.
- 3.2.10 Patients who require chronic treatment with strong CYP3A4/5 inhibitors ≤ 14 days prior to registration are not eligible.

*NOTE: See Appendix I for examples of such medications. Patients who are currently on treatment with strong CYP3A4/5 inhibitors may be eligible if they are able to be switched to an alternative therapy that is not a strong CYP3A4/5 inhibitor prior to registration on study.*

- 3.2.11 Patients with a history of allergic reactions attributed to compounds of similar chemical or biologic composition to ibrutinib are not eligible.
- 3.2.12 Patients with uncontrolled intercurrent illness including, but not limited to, any of the following are not eligible:
  - Ongoing or active systemic infection
  - Symptomatic congestive heart failure
  - Myocardial infarction within 6 months prior to registration
  - Unstable angina pectoris
  - Uncontrolled or symptomatic cardiac arrhythmias
  - Any Class 3 (moderate) or Class 4 (severe) cardiac disease as defined by the New York Heart Association Functional Classification
  - Psychiatric illness/social situations that would limit compliance with study requirements.
- 3.2.13 Patients who have any life-threatening illness, medical condition, or organ system dysfunction which, in the investigator's opinion, could compromise the subject's safety, interfere with the absorption or metabolism of ibrutinib capsules, or put the study outcomes at risk are not eligible.
- 3.2.14 Patients with a *known* HIV infection are not eligible (HIV testing not required).
- 3.2.15 Patients with a *known* JC virus infection and/or progressive multifocal leukoencephalopathy (PML) are not eligible.
- 3.2.16 Patients with clinically active hepatitis A, B, or C infections are not eligible.  
Note: Patients with a history of hepatitis may be eligible if they have a normal titer. Such cases should be approved by the study PI.
- 3.2.17 Female patients who are pregnant and/or lactating are not eligible.

Study Numbers: NU 14H06  
PCI-32765MCL2003Initial version: September 24, 2014  
AMD 11: ver. date 08.06.2022

*NOTE: It is not known whether ibrutinib or its metabolites are excreted in human milk. Because many drugs are excreted in human milk and because of the potential for serious adverse reactions in nursing infants from ibrutinib, breastfeeding should be discontinued during ibrutinib treatment.*

## 4.0 TREATMENT PLAN

### 4.1 Overview

Induction therapy will not be part of the protocol-specified treatment. Patients must have received four (4) or more cycles of R-CHOP (with or without alternating R-DHAP), R-Hyper-CVAD, or bendamustine + rituximab (all with or without auto SCT), with documented PR or CR by Cheson 2007 criteria. Within 14 days of study registration, patients will begin treatment with ibrutinib at a fixed dose of 560 mg PO daily. One cycle will be defined as 28 days. Patients may continue to receive cycles of ibrutinib therapy up to 4 years in the absence of progression of disease or intolerable toxicity, or patient preference (including withdrawal of consent).

### 4.2 Administration

Ibrutinib will be administered orally at a dose of 560 mg daily. Patients will be instructed to take 4 140mg capsules for a dose of 560 mg. Ibrutinib is to be taken in the morning (around the same time each day) with approximately 8 ounces (240 mL) of water. All 4 capsules should be taken at the same time and the capsules should remain intact. Subjects should not attempt to open capsules or dissolve them in water.

Subjects should avoid consuming food and beverages containing grapefruit, Star fruit, or Seville oranges for the duration of the study due to CYP 3A4/5 inhibition. The study drug should be taken at roughly the same time each day. If a dose is missed, it can be taken anytime later that same day, with a return to the normal schedule the following day. In general, vomited doses should not be made up, however patients should contact their physician to discuss such cases.

Subjects will be given a study calendar on which to record all taken, missed, or skipped doses for the first 6 cycles of study treatment. The calendar will be returned for review with a member of the study team at scheduled visits to assess compliance in addition to pill counts. During the first 6 cycles, ibrutinib will be dispensed at the beginning of each 28-day cycle. Subjects will be provided with 2 days overage (30 days' worth total) each time study drug is dispensed to allow for delays in scheduling of return visits. After the initial 6 cycles of treatment, visits will be conducted every 3 months and a sufficient drug supply will be dispensed at each visit to last until the next visit. If after 2 years a patient is clinically stable without significant adverse events and lives far from the study site, he or she may elect to be seen by the study investigator every 6 cycles with local clinic visits every 3 cycles in between. In such cases, a 6-month drug supply may be dispensed, however this supply should be given in moderation only for patients who live far away or are otherwise inconvenienced by quarterly study visits. Patients will continue maintaining a study calendar/pill diary for the duration of treatment.

Study staff will instruct subjects on how to store ibrutinib for at-home use as indicated for this protocol (e.g. in a secure location, away from children).

#### **4.3 Toxicity Management & Dosing Holds/Dose Modifications**

##### **4.3.1 Dose Holds**

At each study visit (see section 5.0 for schedule), the subject will be evaluated for possible drug toxicities. All previously established or new toxicities observed at any time are to be recorded in the appropriate electronic case report form (eCRF) and managed as described below. The lead principal investigator and QAM should be contacted regarding any unmanageable toxicity.

Study drug may be held for a maximum of 28 consecutive days. Once the ibrutinib dose is reduced, it cannot be re-escalated. When a dose is missed or held, it will not be made up, regardless of duration.

Observations and scheduled assessments will continue regardless of amount of drug the patient has had and should always be based on time from C1D1. (For example, if a patient is held on C2D14 for a week, the day they re-start will be C2D21, and the patient will still have scheduled assessments as planned on C3D1) Please contact QA if you have any questions on timing of holds or study assessments.

*See section 4.4.3 for subjects requiring the initiation of anticoagulants while receiving study drug and for instructions on dose modifications or temporary hold during concomitant administration of CYP3A4/5 inhibitors or inducers. For guidance on dose hold during the perioperative period for subjects who require surgical intervention or an invasive procedure while receiving study drug please see section 4.4.4.*

##### **4.3.2 Dose Modifications**

The actions described below should be followed for the indicated drug- related toxicities per Table 4-1:

- Grade 3 (ANC <1000/mm^3) or Grade 4 neutropenia (ANC <500/mm^3)
- Grade 3 thrombocytopenia (platelets <50,000/mm^3) in the presence of significant bleeding
- Grade 4 thrombocytopenia (platelets <25,000/mm^3)
- Grade 3 or 4 neutropenia with infection or fever
- All other Grade 4 hematological toxicities
- Grade 3 or Grade 4 non-hematological toxicities including nausea, vomiting or diarrhea (if persistent despite optimal antiemetic or antidiarrheal therapy), exceptions noted below for cardiac related toxicities (see [Sections 4.3.2.1 & Section 4.3.2.1.1](#))
- Grade 2 cardiac failure
- Any unmanageable Grade 2 or Grade 3 drug-related toxicities. The PI should be contacted in these cases.

Table 4-1 Dose Modification Actions	
Occurrence	Action
First	Hold ibrutinib until recovery to ≤ Grade 1 or baseline; restart at 420 mg dose
Second	Hold ibrutinib until recovery to ≤ Grade 1 or baseline; restart at 280 mg dose
Third	Discontinue ibrutinib

 When ibrutinib doses are held they will not be made up – study assessments will continue as originally scheduled. Ibrutinib may be held for a maximum of 28 consecutive days at a time. Study treatment should be permanently discontinued in the event of a toxicity lasting >28 days. Once the ibrutinib is reduced it cannot be re-escalated.

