##### **4.4.3 Concomitant Medications/Treatments Requiring Special Precautions**

###### **4.4.3.1 CYP3A4/5 Inhibitors/Inducers**

Study Numbers: NU 14H06  
PCI-32765MCL2003Initial version: September 24, 2014  
AMD 11: ver. date 08.06.2022

Ibrutinib is metabolized primarily by CYP3A4/5. The clinical significance of the potential drug-drug interaction with strong CYP3A4/5 inhibitors in oncology subjects is currently not known. Due to this potential increase in ibrutinib exposure, concomitant use of strong CYP3A4/5 inhibitors (such as, indinavir, nelfinavir, ritonavir, saquinavir, clarithromycin, telithromycin, ketoconazole, itraconazole, and nefazodone; see Appendix I for a comprehensive list of such medications) should be avoided while the subject is receiving treatment and at least 14 days prior to registration. Moderate CYP3A4/5 inhibitors (aprepitant, erythromycin, fluconazole, verapamil, and diltiazem) should be used with caution. Grapefruit juices, Star fruit, and Seville oranges may also increase ibrutinib plasma concentrations and should be avoided for the duration of ibrutinib treatment.

If use of a strong CYP3A inhibitor is indicated, selection of an alternate concomitant medication with less potent enzyme inhibition potential is strongly recommended. If ibrutinib must be administered with a strong or moderate CYP3A inhibitor, refer to Table 4-3 for recommended dose modifications for ibrutinib, and notify the PI and NU Quality Assurance Monitor (QAM). Subjects should be monitored closely for potential treatment-related toxicities. After discontinuation of the CYP3A inhibitor, the same dose of ibrutinib that was administered prior to the temporary hold may be given upon reinitiation of ibrutinib.

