**Table 4-3: Dose Modifications for Use with CYP3A Inhibitors**

Patient Population	Coadministered Drug	Recommended Ibrutinib Dose
B-Cell Malignancies	• Moderate CYP3A inhibitor	280 mg once daily  Modify dose as recommended per Table 4-1, Table 4-2 and Section 4.3.2.1.1.
	• Voriconazole 200 mg twice daily • Posaconazole suspension 100 mg once daily, 100 mg twice daily, or 200 mg twice daily	140 mg once daily  Modify dose as recommended per Table 4-1, Table 4-2 and Section 4.3.2.1.1.
	• Posaconazole suspension 200 mg three times daily or 400 mg twice daily • Posaconazole IV injection 300 mg once daily • Posaconazole delayed-release tablets 300 mg once daily	70 mg once daily  Interrupt dose as recommended per Table 4-1, Table 4-2 and Section 4.3.2.1.1..
	• Other strong CYP3A inhibitors	Avoid concomitant use.  If these inhibitors will be used short-term (such as anti-infectives for seven days or less), interrupt ibrutinib.
	• Moderate CYP3A inhibitor	420 mg once daily  Modify dose as recommended per
Chronic Graft versus Host Disease		

Study Numbers: NU 14H06  
PCI-32765MCL2003Initial version: September 24, 2014  
AMD 11: ver. date 08.06.2022

		Table 4-1, Table 4-2 and Section 4.3.2.1.1..
	
 
• Voriconazole 200 mg twice daily
 
• Posaconazole suspension 100 mg once daily, 100 mg twice daily, or 200 mg twice daily
 
	280 mg once daily  Modify dose as recommended per Table 4-1, Table 4-2 and Section 4.3.2.1.1..
	
 
• Posaconazole suspension 200 mg three times daily or 400 mg twice daily
 
• Posaconazole IV injection 300 mg once daily
 
• Posaconazole delayed-release tablets 300 mg once daily
 
	140 mg once daily  Modify dose as recommended per Table 4-1, Table 4-2 and Section 4.3.2.1.1..
	
 
• Other strong CYP3A inhibitors
 
	Avoid concomitant use.  If these inhibitors will be used short-term (such as anti-infectives for seven days or less), interrupt ibrutinib.

Coadministration of ibrutinib with strong CYP3A4/5 inducers (such as carbamazepine and rifampin) may decrease ibrutinib plasma concentrations and should be avoided. A comprehensive list of inhibitors, inducers, and substrates is provided in a link in Appendix I.

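### For patients on a CYP3A inhibitor, the fixed restart doses in Tables 4-1 and 4-2 conflict with either the no-re-escalation rule or Table 4-3, and no sentence says which dose governs

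*Combined protocol and SAP*

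**What the plan says.** Section 4.3.2, Table 4-1, applies after listed drug-related toxicities, mostly Grade 3 or 4. Ibrutinib is held until recovery to at most "Grade 1 or baseline; restart at 420 mg dose" at the first occurrence, and to at most "Grade 1 or baseline; restart at 280 mg dose" at the second; the third means discontinuation. Table 4-2 (section 4.3.2.1, Grade 3 arrhythmias) uses the same 420 mg restart once, then discontinuation. Footnote 1 of both tables adds "Once the ibrutinib is reduced it cannot be re-escalated", and section 4.3.1 states the rule again: "Once the ibrutinib dose is reduced, it cannot be re-escalated".

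Table 4-3 (section 4.4.3.1) sets the dose for B-cell malignancies while an inhibitor is taken: 280 mg with a moderate inhibitor, and 140 mg with voriconazole or the lower posaconazole suspension doses. Both rows then say "Modify dose as recommended per Table 4-1, Table 4-2 and" section 4.3.2.1.1. A third row, 70 mg with higher-dose posaconazole, is worded differently: "Interrupt dose as recommended per Table 4-1, Table 4-2 and" the same section.

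Moderate inhibitors are permitted: "Moderate CYP3A4/5 inhibitors (aprepitant, erythromycin, fluconazole, verapamil, and diltiazem) should be used with caution". Exclusion 3.2.10 covers only chronic treatment with strong ones. After an inhibitor is stopped, section 4.4.3.1 says that "the same dose of ibrutinib that was administered prior to the temporary hold may be given upon reinitiation of ibrutinib".

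**The concern.** The restart doses are absolute amounts, not steps down from the dose the patient was taking. From 560 mg, both 420 mg and 280 mg are reductions. For a patient already at 280 mg or 140 mg because of an interaction, Table 4-3 points to entries that mostly lie above the current dose.

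A site that followed the restart cell as printed would raise the dose just after a drug-related toxicity, while the inhibitor that prompted the lower dose was still being taken. The 280 mg row can arise without any protocol deviation, because moderate inhibitors are allowed on study. The stake is individual dosing safety and consistency between sites, not the primary analysis.

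**Working it through.** The plan states no figure to reproduce here. The check compares doses entry by entry and then reads the rules against each other.

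**Inputs.** Full dose 560 mg (section 4.2). Restart doses 420 mg and 280 mg (Table 4-1) and 420 mg (Table 4-2). Interaction doses 280 mg and 140 mg (Table 4-3, B-cell rows). Assumption: the inhibitor is still being taken at restart.

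**Step 1. Ratio = restart dose / Table 4-3 dose.**

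| Table 4-3 dose | Restart dose | Ratio | Result |
|---|---|---|---|
| 280 mg | 420 mg (Tables 4-1 and 4-2, first) | 420/280 = 1.5 | above |
| 280 mg | 280 mg (Table 4-1, second) | 280/280 = 1 | equal |
| 140 mg | 420 mg (Tables 4-1 and 4-2, first) | 420/140 = 3 | above |
| 140 mg | 280 mg (Table 4-1, second) | 280/140 = 2 | above |

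Three of four distinct pairs are above, one is equal and none is lower. Counting printed cells gives 2 × 3 = 6, of which 5 are above, but only because Table 4-2 repeats the 420 mg entry. The distinct-pair count is the fairer one.

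**Step 2. Which rule governs?**

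- *Interaction reductions count under the no-re-escalation rule.* The three higher restarts are then barred by the footnote attached to the column that prints them. This reading also leaves it unclear whether a patient lowered to 280 mg for a short inhibitor course may ever return to 560 mg. The only text on going back is worded for a hold, not for a reduction.
- *Only toxicity reductions count.* The footnote is then silent, and the three higher restarts contradict the dose that Table 4-3 sets for the continuing inhibitor.
- *The inhibitor is started during the toxicity hold.* No reduction has yet been made at a first occurrence, so the no-re-escalation rule has nothing to act on. With a moderate inhibitor, Table 4-1 says 420 mg and Table 4-3 says 280 mg. This is plausible: neutropenia with infection is a listed trigger, and fluconazole and erythromycin are named moderate inhibitors.

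Each reading leaves a conflict, and no sentence ranks the tables.

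**Step 3. Effect of a lower-of cap.** min(420, 280) = 280; min(280, 280) = 280; min(420, 140) = 140; min(280, 140) = 140. None of the four pairs then exceeds the Table 4-3 dose. All four equal it, so the cap stops escalation but gives no reduction after the toxicity.

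**Step 4. Inhibitor already stopped at restart.** 420/560 = 0.75 and 280/560 = 0.5. Measured against the full dose, both are true reductions, and Table 4-3 no longer applies.

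**The 70 mg row** is left out of the count because it tells the site to interrupt. If the table restarts were applied after that interruption, the ratios would be 420/70 = 6 and 280/70 = 4, but the text does not say that they are.

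**The case against.** The strongest reply is that the plan already blocks the higher dose. The no-re-escalation rule appears three times, has no exception for interactions, and qualifies the very cells at issue. Read literally, it gives a patient already at 280 mg or 140 mg the same restart as the proposed cap. Table 4-3 also does not lapse after a hold, and section 4.4.3.1 requires notice to the principal investigator and the quality assurance monitor, with close monitoring.

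Much of this stands. A reader might infer that the protocol directs sites to escalate after toxicity, or that nothing in it restrains the higher dose. The documents do not support either inference: a site would have to follow the cell over both its footnote and Table 4-3. What survives is that the protection rests on inference. The rule does not define which reductions count, it contradicts the entries it annotates, and it does not reach an inhibitor started during a first-occurrence hold. The notification duty names no dose.

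Appendix IV says these tables follow prescribing information of May 2022 and an investigator letter. Neither is available here, so whether they address the interaction cannot be checked.

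A reader might also try to size the problem from section 1.2.3: 36 × 0.458 = 16.5 patients with Grade 3 or 4 events, times some share on inhibitors. The documents do not support this. The 45.8% comes from other studies and is not limited to drug-related events. It includes events such as Grade 3 anemia, which the trigger list does not name. No inhibitor-use rate is given.

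**Conclusion.** The point holds as an internal contradiction in the dosing instructions. While an inhibitor continues, three of the four distinct pairs in the 280 mg and 140 mg rows restart above the Table 4-3 dose, by factors of 1.5 to 3, and none restarts below it. The conflict is with the no-re-escalation rule or with Table 4-3, depending on a reading that the text leaves open.

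Few patients are likely to be affected. Appendix IV dates the current Table 4-1 and the new Table 4-2 to Amendment 11 (August 2022), so only patients still on ibrutinib from then on are exposed to this wording, and their number is not given. The arithmetic is certain; which dose sites would actually choose is not. The endpoint, sample size, error rates and analysis are unaffected.

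**What to change.** Add to footnote 1 of Tables 4-1 and 4-2: *While a CYP3A inhibitor continues, never restart above the Table 4-3 dose; use the lower of the two.*

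In sections 4.3.1 and 4.4.3.1, state whether a reduction made only for an inhibitor may be reversed after it stops. If it may, limit the return to the Table 4-1 or 4-2 dose for any toxicity that occurred meanwhile.

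The sponsor should separately decide whether such a patient, having had a listed toxicity, should step down further or discontinue; the cap does not settle this. It should also say what follows the interruption in the 70 mg row, where supply in 140 mg capsules taken intact (sections 4.2 and 8.1.6) raises its own question.

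The cost is one footnote sentence in two tables, a clarification in two sections, a site memo and those clinical decisions. No statistical element changes.
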